Discrete Choice. Interdisciplinary research describes choice as a function of the relative expected value of the options at hand.^{61, 62} Further, an option’s anticipated value is derived from the integrated values of its individual attributes.^{63, 64} Widely used in consumer research, discrete choice experiments (DCEs) reveal the extent to which individual product attributes determine choice.⁶⁵ In DCEs, across several trials, participants chose their preferred option from a selection of products, each described as a set of attributes. The products/combinations of attributes presented in each trial are experimentally varied such that the relative importance of each attribute can be discerned using logistic regression. In tobacco regulatory science DCEs have been used

frequently to evaluate general preferences for cigarette and vaping device characteristics.⁶⁶⁻⁶⁹ Here, we will use the DCE method to investigate the contribution of nicotine content and flavor availability to choices between cigarettes and vaping devices.

OBJECTIVES

We are proposing a four condition ETM study to determine if banning NNC is sufficient for encouraging smokers to switch to potentially less harmful products or if the availability of higher nicotine and/or flavored alternative products (specifically e-cigarettes) are needed to achieve maximal reductions in smoking.

METHODS AND MEASURES

Overall Study Design

We propose to conduct a within-subjects, multi-session virtual lab study and validation field assessment to determine how the availability of flavored e-liquids affects product purchasing among cigarette smokers. Adult daily cigarette smokers (N=64) will be recruited for this study. After initial eligibility is assessed, participants will complete six virtual sessions (1 baseline, 4 experimental, and 1 follow-up) and three in person sessions with one field assessment to evaluate their tobacco use.

Design and Setting

Participants will be recruited from Winston-Salem, NC and the surrounding area using advertisements on public transit, community flyers, and social media.. In-person lab visits to drop off biosamples and pickup study products will be conducted at the Wake Forest Tobacco Control Center of Excellence located in Biotech Place in the Innovation Quarter.

Subject Selection Criteria

We anticipate recruiting up to 100 participants to achieve 64 completers.

Inclusion criteria:

1. 21+ years of age

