Participants will undergo one of four marketplace conditions during Virtual Visits 2-5, with the order of administration randomized across participants.

- Marketplace Condition 1 includes moderate nicotine content vape with all flavor e-liquids.
- Marketplace Condition 2 includes moderate nicotine content vape with tobacco e-liquids.
- Marketplace Condition 3 includes low nicotine content vape with all flavor e-liquids.
- Marketplace Condition 4 includes low nicotine content vape with tobacco e-liquids.

Staff will instruct participants to complete the ETM task as if they are purchasing the products from a retailer, and that one iteration of the task will be randomly selected and will determine which products they will use during the field assessment. In reality, we will randomly assign which condition is used (Condition 2 or 4) but will assign products based on when NNC were not available to simulate a nicotine content reduction policy.

For each marketplace condition, participants will complete 7 iterations of the ETM task in ascending order. The prices for NNC cigarettes on the ETM will be set at: \$0.12, \$0.25, \$0.50, \$1.00, \$2.00 per cigarette; in the 1st ETM condition, NNC cigarettes will be set at \$0.25 with no VLNC available to purchase to simulate current market status; while in the 6th ETM condition, NNC will be eliminated from the marketplace to simulate a nicotine content reduction policy. The costs for the other products will reflect average prices in NC and will not change during the task. For each task iteration, participants will receive individually-tailored account balances approximately equal to the money they would spend on cigarettes for seven days. They can purchase as many or few products as their account balance allows. Participants are not required to buy products from the ETM or can buy nicotine gum if they prefer. If they do not buy products from the ETM and do not use tobacco products during the field assessment, then they will receive their ETM account balance at Virtual Visit 6. This payment is delayed to reduce the likelihood that they will use this money to buy their preferred brand cigarettes, thus decreasing the validity of the ETM task.

Participants will be instructed to use only the products purchased from the ETM during the subsequent 7-day period after Virtual Visit 5 and told that we will assess adherence at Lab Visit 3.

In-Person Lab Visit 2

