Participants will be paid \$160 for completing the study. They will earn \$30 for completing Virtual Visit 1, \$15 per visit for completing Virtual Visits 2-5, \$20 for Virtual Visit 6, plus a \$50 bonus for completing the study. Participants who do not meet enrollment criteria at Virtual 1 will earn \$20 for attending the visit. Participants who start but do not complete the study will receive payments for the virtual visits attended. They will not receive the \$50 completion bonus. Participants will also be reimbursed up to \$20 per in-person lab visit for transportation costs.

ANALYSIS PLAN

Primary Outcome

- Number of cigarettes purchased (analyzed as raw data and using derived behavioral economic measures).

Secondary Outcomes

- E-liquid purchased (analyzed as raw data and using derived behavioral economic measures).
- Relative importance and utility data from discrete choice experiment
- Perceived Health Risk Scale scores
- Product Evaluation Scale scores
- Minnesota Nicotine Withdrawal Scale scores
- Questionnaire on Smoking Urges scores
- Tobacco Product Interest scores
- Tobacco Policy Questionnaire scores

Exploratory Outcomes

- Themes emerging from the qualitative interviews
- Product use during Field Assessment
- Biomarkers of exposure during Field Assessment

Sample Size/Estimation/Analysis

Statistical analysis plan

This ETM study will use a 2x2 factorial design. The primary objective will be to evaluate the effect of the two factors – e-liquid nicotine content (moderate vs. low) and e-liquid flavors (all flavors available vs. only tobacco flavor) – on purchasing behavior during virtual visits 2 – 5. Product use behavior, biomarkers of exposure, and other measures of smoking behavior during the field assessment will be evaluated in exploratory analyses.

Analysis of the Primary Outcome

The primary outcome will be the number of cigarettes purchased during the virtual visits. These data will be analyzed both in their raw form (i.e. the raw number of cigarettes purchased) and using derived behavioral economic measures. This is a within-subject design, with each participant providing data under all four factor combinations, and, for the raw data, each participant will provide data for all price combinations nested within a visit.

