Raw data will be analyzed using a linear mixed-effects model that includes main effects for e-liquid nicotine content (low vs. moderate), e-liquid flavors (all vs. tobacco only), visit, price condition (analyzed as a categorical variable), and a carryover effect for the previous visits condition (treated as a four-level categorical variable, and random effects for participant and visit nested within participant. This will account for correlation from multiple observations from the same participant, both within and across visits. We will also evaluate whether there is an interaction between the e-liquid nicotine content and e-liquid flavors factors. If significant, the interaction will be included in the model; otherwise, it will be removed. The analysis of derived behavioral economic measures will follow an analogous approach, except that for each measure, there will only be a single outcome for visit. As a result, our linear mixed-effects model will not include a main effect for price condition, and there will only be a single random effect for each participant. Behavioral economic measures will be derived by generating demand curves using an exponential demand equation. Specific measures considered will include: Alpha - the rate of change in demand, and Q_0 – peak consumption. For all analyses, assessments of key model assumptions will be completed and we will consider transformations or alternate analytic approaches if these assumptions are violated.

Analysis of Secondary Outcomes

The analysis of secondary endpoints will be analogous to the analysis described above for the primary endpoints. The amount of e-liquid purchased will be analyzed both as the raw data for each price condition and using derived behavioral economic measures. The analysis of these endpoints will be completed using linear mixed-effects models with the fixed and random effects terms described above. The analysis of the various scales and scores collected at each visit will follow the same approach as the analysis of derived behavioral economic measures described above. As before, assessments of key model assumptions will be completed and we will consider transformations or alternate analytic approaches if these assumptions are violated.

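### The raw-data purchasing models have no participant-by-price random effect, so price-condition intervals, including for removing normal-nicotine cigarettes, are too narrow by a factor that can approach one half

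*Combined protocol and SAP*

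**What the plan says.** All references are to the combined protocol and SAP.

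- **Design (Analysis of the Primary Outcome; Virtual Visits 2-5).** The study is within-subject, with "each participant providing data under all four factor combinations". Within each marketplace condition, "participants will complete 7 iterations of the ETM task in ascending order", and for the raw data "each participant will provide data for all price combinations nested within a visit". The iterations cover five NNC prices from $0.12 to $2.00 per cigarette, one current-market iteration (NNC at $0.25, no very low nicotine cigarettes) and one with NNC removed. Price condition is therefore crossed with visit within each person.
- **Budgets (Virtual Visits 2-5).** In each iteration, "participants will receive individually-tailored account balances approximately equal to the money they would spend on cigarettes for seven days".
- **Model (Analysis of the Primary Outcome).** The fixed effects include "price condition (analyzed as a categorical variable"), and the random effects are "random effects for participant and visit nested within participant". The assurance given is "This will account for correlation from multiple observations from the same participant, both within and across visits". Analysis of Secondary Outcomes uses the same terms for raw e-liquid purchases.
- **Aims.** The Objectives section wants "to determine if banning NNC is sufficient for encouraging smokers to switch to potentially less harmful products". The Statistical analysis plan section makes e-liquid nicotine content and flavor availability the primary objective. No test or interval for NNC removal is prespecified.
- **Safeguard.** Assumptions will be checked, and transformations or other approaches considered. No diagnostic for the covariance structure and no specific remedy is named.

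**The concern.** Under the planned random effects, two purchases by one person on different visits have the same correlation whether they were made at the same price or at different prices. Personal budgets and a price range of about 17-fold (2.00/0.12 = 16.7) make that implausible. What a person can afford at each price differs between people and persists across visits, and so may willingness to buy very low nicotine cigarettes once NNC are gone. The plan itself derives Alpha, the rate of change in demand, for each visit, so it measures individual price response elsewhere.

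Stable participant-by-price variation then falls into the residual, and the model treats 4 x 64 = 256 readings per price condition as if, apart from the participant and visit effects, they were independent. Price condition is the raw-data model's only term that bears on what removing NNC does, so a finding on cigarettes or e-liquid under the ban could carry an interval that is too narrow. The inflated residual can also distort the standard errors of the two primary factors, in the opposite direction.

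**Working it through.** **The plan's own figures.** The documents give no interval width, standard error or variance component for price contrasts. The only related figures are the detectable main effects under Power calculation: 0.49, 0.45 and 0.41 at within-participant correlation r = 0.0, 0.4 and 0.8. Assuming two-sided 5% (no alpha is stated), total variance 1 and one value per visit, a factor effect averaged over the other factor has SE sqrt((1-r)/64). Multiplying by 1.96 + 0.84 gives 0.35, 0.27 and 0.16. The stated figures are not reproduced. The simulation model is not described and its figure is not shown, so this is a separate matter, and nothing below depends on it.

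**Inputs.** N = 64 completers, 4 visits, 7 price conditions (documents). Assumed true structure: participant + visit within participant (variance V) + participant-by-price (W) + error (E), with rho = W/(W+E). V, W and E are assumptions, so ranges are shown.

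**Price contrast (for example NNC removed versus current market).**

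- Planned SE squared: 2(W+E)/(64 x 4), because the residual absorbs W.
- Correct SE squared: 2(W+E/4)/64, because W does not average out over visits.
- Width ratio: sqrt((W+E)/(4W+E)) = 1/sqrt(1+3rho).
- Coverage of a nominal 95% interval: 2 x Phi(1.96 x ratio) - 1.

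| rho | planned / correct width | coverage |
|---|---|---|
| 0.1 | 0.88 | 91.4% |
| 0.3 | 0.72 | 84.5% |
| 0.5 | 0.63 | 78.5% |
| 0.8 | 0.54 | 71.2% |
| 1.0 (limit) | 0.50 | 67.3% |

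Mixed-model fits of the full specification (visit, price and carryover terms; about 100 data sets per setting) agree. The mean planned SE was 0.087 against a correct 0.140 (ratio 0.62) at rho 0.5, and 0.086 against 0.163 (0.53) at rho 0.8. Balanced simulation with error SD 1 gave false-positive rates of about 11-13%, 21-23% and 28-31% at participant-by-price SD 0.5, 1 and 2 (rho 0.2, 0.5 and 0.8). An illustrative budget-constrained count model with unequal variances, all inputs assumed, gave ratios from 0.38 to 0.86.

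**Flavor and nicotine.** Participant-by-price effects are the same at every visit, so they cancel from visit-to-visit contrasts. The visit-within-participant mean square has expectation 7V+E, and the planned residual mean square has expectation W+E. If 7V is at least W, the visit variance is estimated above zero and the SE is about right. If 7V is below W, the visit variance estimate tends to be truncated at zero and the SE comes from the pooled mean square, which is too large.

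| V, W, E | planned SE / true SE |
|---|---|
| 0.20, 0.5, 0.5 | 1.04 |
| 0.10, 0.5, 0.5 | 1.04 |
| 0.05, 0.5, 0.5 | 1.07 |
| 0.05, 0.8, 0.2 | 1.35 |
| 0, 0.8, 0.2 | 2.1 |

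**Effect on power.** Take error SD 1 and ignore the small cost of the factor and carryover terms. Degrees of freedom are 64 x 3 - 3 = 189 for visit within participant and 1,792 - 256 - 6 = 1,530 for the residual. Take visit SD 0.3 (V = 0.09) and participant-by-price SD 2 (W = 4):

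- True SE: sqrt((0.09 + 1/7)/64) = 0.0603. The effect with 80% true power is 2.80 x 0.0603 = 0.169.
- Pooled mean square: (5 x 1,530 + 1.63 x 189)/1,719 = 4.63. Planned SE: sqrt(4.63/(7 x 64)) = 0.102.
- Power: P(Z > (1.96 x 0.1017 - 0.1689)/0.0603) = P(Z > 0.50), about 31%. Simulation gave about 33%.

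The same steps give 59% at visit SD 0.5 with participant-by-price SD 2 (simulation about 60%), and 74% at visit SD 0.3 with SD 1 (simulation 74%). At visit SD 1, simulation showed no loss with participant-by-price SD up to 2.

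**The case against.** **The size depends on an unknown.** A reader might infer that the NNC-removal interval simply is half its correct width. The documents do not support that: they give no variance components, and in the equal-variance algebra one half is the limit at rho = 1. This part of the objection stands.

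**The affected contrast is not the primary one.** The SAP names the two e-liquid factors as primary and never says it will report an interval for NNC removal. This also stands, and it lowers the severity. It does not remove the point, because the Objectives section asks whether banning NNC is enough, and price condition is the raw-data term that would answer it.

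**Harm to the primary factors is conditional.** A reader might infer a general loss of power for flavor and nicotine. The large losses above need participant-by-price variance about 16 to 44 times the visit variance (4/0.25 and 4/0.09). The error there is also conservative and does not create false-positive factor effects. Alpha and Q0 have one value per visit and no price term, so they do not have the problem.

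**The correlation sentence is not simply false.** The participant intercept does induce correlation across visits, and the visit term adds correlation within a visit. What is missing is the extra correlation at the same price. Tailored budgets make that extra correlation likely but do not prove its size.

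**Assumption checks might catch it.** A log transformation could move proportional budget differences into the participant intercept. It would not absorb differing acceptance of very low nicotine cigarettes, and no transformation supplies the missing covariance term. The promised checks name no remedy, so this answers the point only in part.

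**Conclusion.** The point holds with its size left open; it is a should-fix. Both raw-data models omit stable participant-by-price variation, and the plan's assurance about correlation is too strong. Price-condition intervals are too narrow by 1/sqrt(1+3rho): 0.88 of the correct width at rho 0.1, 0.63 at 0.5, and 0.50 at the limit. This assumes 4 complete visits and equal variances across price conditions. Unequal variances could move the ratio either way.

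For flavor and nicotine, standard errors are about right unless 7 x visit variance falls below the participant-by-price variance, in which case they are too large and power is lost. The documents do not show which case applies. They therefore support neither a fixed one-half figure nor a claim that the primary factor tests are generally compromised.

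**What to change.** In Analysis of the Primary Outcome, and for raw e-liquid purchases in Analysis of Secondary Outcomes:

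1. Add a random intercept for participant-by-price-condition, crossed with visit, to the two existing random effects.
2. Report participant-clustered robust standard errors with a small-sample correction (64 clusters). These also protect against unequal variance across prices, which a single added variance component does not.
3. State a fallback if the model does not converge: test price-condition and factor effects as participant-level contrasts with their own standard errors.
4. Reword the correlation sentence to match the revised structure.

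The cost is one model term and a few sentences in the SAP, with no new data and no design change. Intervals for price and NNC-removal effects become wider, which is their correct width. If participant-by-price variance proves small, little changes.

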1. Identifying Information Form will include the participant's Subject Identifier, name, address (including the county of residence), email address, phone number, age, and date of birth.
2. Tobacco Use History and Exposure Questionnaire, which measures variables such as smoking amount, cigarette brand, age of initiation of smoking, number of quit attempts, duration of quit attempts and duration of smoking.
3. Concomitant Medications Form will assess current medication usage.

The following screening surveys will be self-administered via REDCap:

1. Brief Medical History Questionnaire to query current diagnoses, symptoms and past health problems.
2. Demographic History Questionnaire, which will assess age, gender, ethnicity, race, education, income, marital status, living situation, and employment history.
3. Contemplation Ladder³⁴ to assess intention to quit smoking.

Fagerstrom Test for Cigarette Dependence³⁵ (FTCD) to assess nicotine dependence levels. In the event that the REDCap websites are not functioning, the virtual visits will be rescheduled to a later date and time.

Eligibility Determination

Research staff will determine eligibility after reviewing all criteria, sans the expired breath carbon monoxide reading and pregnancy test. Researchers will pay ineligible participants \$20 for their time spent completing the screening surveys. Eligible participants will complete additional surveys and will receive an extra \$10 for their time.

The following baseline assessments for eligible participants will be administered as an interview and entered into REDCap by the interviewer:

1. Timeline Follow Back (TLFB) Questionnaire,³⁶ which will assess past 14-day tobacco and nicotine product use. If a participant's reported cigarette use on the TLFB conflict with their reporting on the Tobacco Use History and Exposure Questionnaire, the RA will point out the discrepancy to the participant and ask whether they would like to modify their responses on the Tobacco Use History and Exposure Questionnaire or clarify why they are discrepant (e.g., participants had an upper respiratory infection in the past week that resulted in atypical smoking behavior).

The following surveys will be self-administered using REDCap:

1. Tobacco Policy Questionnaire (adapted from International Tobacco Control (ITC) – Four Country survey) which assess support for various tobacco control policies, including banning menthol flavoring in cigarettes and e-cigarettes.

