2. Perceived Health Risks Scale, a measure of the perceived addictive potential and other health risks associated with cigarettes, e-cigarettes and nicotine gum
3. Tobacco Product Interest Scale, a visual analog scale assessing interest in use of various tobacco and nicotine products
4. Environmental/Social Influence on Tobacco use to assess environmental and social impacts on tobacco use.

In-Person Lab Visit 1

After completing Virtual Visit 1, participants will complete the COVID screener within 24 hours of their Lab visit via email or phone. Research staff will wear personal protective equipment including face masks and gloves. The participants will be required to wear facemasks when interacting with the staff. If participants do not have a mask, one will be provided to them to use for the remainder of the study. Temperature checks will be conducted immediately upon arrival using a thermal heat scanner.

Participants will provide carbon monoxide (CO) readings at least 6-feet away from other people, including the research staff, while they have their masks off. NicCheck Strips, which assess cotinine levels in urine, will also be used to confirm smoking status if participants have an expired breath CO reading less than or equal to 8 ppm. Participants with child-bearing potential will complete a urine pregnancy test.

The following surveys will be self-administered using REDCap:

1. Minnesota Nicotine Withdrawal Scale a measure of nicotine withdrawal symptoms
2. Questionnaire of Smoking Urges-Brief – Usual Brand Cigarette, which measures the urge to smoke
3. Cigarette Evaluation Scale, which measures responses to cigarettes (e.g., reward, satisfaction)

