Discrete choice task 1: The Sawtooth Lighthouse Studio platform will host a discrete choice task (See DCE Questionnaire). First, participants will rate the appeal of cigarettes and e-cigarettes characteristics, which helps familiarize them with the product features that will be manipulated in the choice task. Next, the choice task will begin, and they will make several choices between a cigarette option and an e-cigarette option responding to a prompt that asks which they would rather use exclusively for the next week. Each cigarette vs e-cigarette trial will present different combinations of cigarette nicotine content, e-liquid nicotine content, and e-liquid flavor. Finally, the participant will complete follow-up questions about which characteristics most informed their choices. The data from this task will reveal how participants prioritize and make tradeoffs between product type, nicotine content, and flavor when forming preferences.

After completing the discrete choice procedure, participants will also be given the opportunity to sample the low and normal nicotine Spectrum investigational cigarettes available during the ETM (up to 4 puffs each). Other products will also be available on the ETM, but will not be available for sampling. These include: fruit, dessert, menthol, and tobacco flavored e-liquids; and mint, fruit and cinnamon flavored nicotine gum.

Virtual Visits 2-5

Participants will complete Virtual Visit 2 between 1 and 21 days after completing In-Person Lab Visit 1. Virtual Visits 2-5 will ideally be conducted four days in a row to reduce online task fatigue. However, visits may be scheduled up to 7 days apart.

The following assessment will be administered as an interview and entered into REDCap by the interviewer:

1. Timeline Follow Back (TLFB) Questionnaire, which will assess tobacco and nicotine product use since their last virtual visit.

Participants will complete the ETM task on the computer. If the participant needs assistance with navigating the online marketplace the research staff may screen share and allow the participant to verbally select the items that they would like to purchase. The products available on the ETM include:

- Spectrum cigarettes
- Fruit, dessert, mint and tobacco e-liquids (e.g., Vaporesso Xross Mini)
- Mint, fruit, and cinnamon nicotine gum (e.g., Nicorette).

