In-Person Lab Visit 2 will be completed up to 48 hours after completing Virtual Visit 5. Participants will complete the COVID screener within 24 hours of their Lab visit via email or phone. Research staff will wear personal protective equipment during the visit including face masks and gloves. The participants will be required to wear facemasks when interacting with the staff. Temperature checks will be conducted immediately upon arrival using a thermal heat scanner.

Participants will provide CO readings be at least 6-feet away from other people, including the research staff, while they have their masks off.

Participants will be given the products they purchased during the ETM task and will be instructed to only use these products for the next seven days. They will also be given a urine collection cup and instructions for sample collection.

The field assessment validates the ETM task by having participants use the products in the real world, simulating the different regulatory environments. Actual product use enables us to measure their subjective experiences such as withdrawal, craving, or product satisfaction as well as assess changes in carbon monoxide exposure, a biomarker of harm, when using products other than menthol cigarettes. We will conduct between-subjects analyses comparing these secondary outcomes by marketplace condition.

Virtual Visit 6

Participants will complete Virtual Session 6 seven days after completing In-Person Lab Visit 2.

The following baseline assessments will be administered as an interview and entered into REDCap by the interviewer:

1. Timeline Follow Back (TLFB) Questionnaire which will assess past tobacco and nicotine product use since Virtual Visit 5.

The following surveys will be self-administered using REDCap:

1. Tobacco Policy Questionnaire
2. Minnesota Nicotine Withdrawal Scale
3. Questionnaire of Smoking Urges-Brief – Usual Brand Cigarette
4. Product Evaluation Scale – VLNC, E-Cigarette, Gum (whichever product(s) they select)
5. Perceived Health Risks Scale
6. Tobacco Product Interest Scale
7. Health Changes Questionnaire

Participants will complete the ETM task under the same marketplace condition from which they received their field assessment products. Exploratory pre-post field assessment analyses will examine how actual use of the products affects subsequent purchasing of those products.

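### The secondary scale scores are assigned a within-person condition model, but no scale is scheduled at the visits where the marketplace conditions vary

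*Combined protocol and SAP*

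**What the plan says.** Secondary Outcomes lists eight items. Six are scale scores: Perceived Health Risk, Product Evaluation, Minnesota Nicotine Withdrawal, Smoking Urges, Tobacco Product Interest and Tobacco Policy.

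Analysis of Secondary Outcomes gives the rule for them: "The analysis of the various scales and scores collected at each visit will follow the same approach" as the derived behavioral economic measures. Analysis of the Primary Outcome sets out that approach. It is a linear mixed model with nicotine content, flavor, visit and the preceding condition as fixed effects, one outcome per visit and one random effect per participant. It rests on every participant being observed under all four conditions.

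Three other places bear on the point:

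- Virtual Visits 2-5, on what is carried into the field week: "In reality, we will randomly assign which condition is used (Condition 2 or 4", in the plan's numbering. Both are tobacco-flavor-only conditions. Virtual Visit 6 then repeats the marketplace task under that same condition.
- In-Person Lab Visit 2, which says that field use lets the team "measure their subjective experiences such as withdrawal, craving, or product satisfaction" and adds: "We will conduct between-subjects analyses comparing these secondary outcomes by marketplace condition".
- Analysis of Exploratory Outcomes, where the field regression for product use and biomarkers includes both factors, tests their interaction and adjusts for baseline.

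**The concern.** The SAP rule presumes that the scales are collected at each visit. If they are absent from the four visits where the condition changes, the within-person nicotine and flavor contrasts have no data, and neither has a carryover term between consecutive conditions.

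The plan also gives two different analyses for at least some of these scales: within-person in Analysis of Secondary Outcomes and between-subjects in In-Person Lab Visit 2. A reader cannot tell which contrast will be reported for which scale, so the choice could be made after the data are seen.

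Product Evaluation has a further difficulty. It is completed only for products the participant selected, so a comparison by condition is among self-selected raters, and selection may itself differ by condition.

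**Working it through.** **Step 1. When each scale is collected.** From the visit lists in Eligibility Determination (the Virtual Visit 1 baseline surveys), In-Person Lab Visit 1, Virtual Visits 2-5 and Virtual Visit 6:

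| Scale | Before any condition | Virtual Visits 2-5 | Virtual Visit 6 |
|---|---|---|---|
| Tobacco Policy | Virtual Visit 1 | no | yes |
| Perceived Health Risks | Virtual Visit 1 | no | yes |
| Tobacco Product Interest | Virtual Visit 1 | no | yes |
| Nicotine Withdrawal | Lab Visit 1 | no | yes |
| Smoking Urges | Lab Visit 1 | no | yes |
| Product Evaluation | none | no | yes, selected products only |

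The only assessments listed for Virtual Visits 2-5 are the "Timeline Follow Back (TLFB) Questionnaire, which will assess tobacco and nicotine product use since their last virtual visit" and the marketplace task. Lab Visit 1 uses the Cigarette Evaluation Scale, a different instrument from Product Evaluation. Each participant therefore has at most one on-condition score per scale, against four for purchasing.

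**Step 2. Which model terms can be estimated.** Condition 2 is moderate nicotine with tobacco flavor; Condition 4 is low nicotine with tobacco flavor.

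- *Virtual Visit 6 rows; columns intercept, nicotine, flavor, interaction.* With Conditions 2 and 4 only, flavor is constant. Its column is zero or a copy of the intercept, and the interaction is zero or a copy of nicotine. Rank is 2 of 4. With all four conditions in the field, rank is 4 of 4.
- *Adding the pre-condition row (condition coded 0) and a visit column.* With Conditions 2 and 4, flavor is zero or a copy of visit, and the interaction is zero or a copy of nicotine. Rank is 3 of 5 under either coding. With all four conditions, rank is 5 of 5, but every condition contrast is between persons.
- *If the scales were collected at Virtual Visits 2-5.* One participant's four rows alone give rank 4 of 4.

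**Step 3. Precision of what remains.** The plan states no power for the scales. Its within-person main-effect figures (Power calculation, 64 completers, 80% power) are about 0.49, 0.45 and 0.41 at within-participant correlations 0, 0.4 and 0.8. A closed form does not reproduce them:

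- Factorial main effect, 2.80 × √((1−r)/64): 0.35, 0.27, 0.16.
- Simple effect, 2.80 × √(2(1−r)/64): 0.495, 0.38, 0.22.

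The plan's figures come from a simulation whose settings are not shown, so nothing here rests on that mismatch.

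For the between-person comparison I assume 64 completers split equally, two-sided alpha 0.05, 80% power and a baseline correlation r. The multiplier is z(0.975) + z(0.80) = 2.80.

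- Nicotine main effect, 32 versus 32: 2.80 × √((1/32 + 1/32)(1−r²)) = 0.70, 0.61 and 0.50 SD for r = 0, 0.5 and 0.7.
- If all four conditions reach the field (16 per cell), each main effect has the same precision. The interaction, as a difference of differences, is 2.80 × √((4/16)(1−r²)) = 1.40, 1.21 and 1.00 SD.

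**The case against.** The strongest reply is that the plan already contains what is needed. In-Person Lab Visit 2 announces between-subjects comparisons, and its examples match three of the six scales (Withdrawal, Smoking Urges, Product Evaluation). Analysis of Exploratory Outcomes supplies a baseline-adjusted regression on field condition. On this view the defect is one wrong pointer. For those three scales that is fair: the problem is a contradiction between two sections. But the Lab Visit 2 text gives no model and does not clearly reach the risk, interest and policy scales. The exploratory model opens with product use and biomarkers, and its two-factor form itself conflicts with a field week limited to Conditions 2 and 4.

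One could also read the words about collection at each visit as limiting the rule's scope. The rule then covers none of the six scales and leaves them without a model. The SAP's allowance for alternative methods is triggered by violated model assumptions and does not address observations that were never scheduled.

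Three points stand:

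- A mixed model can be fitted to the pre-condition and Virtual Visit 6 scores of five scales, and it still estimates visit and nicotine terms. ANCOVA is one reasonable choice among others.
- The loss of flavor comes from a separate inconsistency and depends on which statement about field conditions is right.
- The detectable differences are illustrative and contradict no stated figure.

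**Conclusion.** The concern holds. None of the six scales is scheduled where conditions vary within a person, so the analysis stated for six of eight secondary outcomes cannot deliver the contrasts it is written for. This follows from the visit lists and needs no numerical assumption.

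The loss of flavor and the interaction for these scales is conditional on only Conditions 2 and 4 reaching the field. If all four do, both terms are estimable, though only between persons. In either case a between-person nicotine contrast remains and, for five scales, so does a pre-post change.

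The detectable nicotine difference of 0.50 to 0.70 SD depends on the assumed equal split, alpha and baseline correlation. The primary outcome and e-liquid purchasing are not touched. This should be fixed before analysis, but it does not threaten the main question.

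**What to change.** First reconcile Virtual Visits 2-5, In-Person Lab Visit 2, Analysis of Secondary Outcomes and Analysis of Exploratory Outcomes on which conditions reach the field. Also confirm whether any scale is meant to be collected at Virtual Visits 2-5. Then take one of two routes.

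**Route A, if the schedule stands.** Replace the sentence on scales in Analysis of Secondary Outcomes with text to this effect:

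> Virtual Visit 6 scores will be compared between participants by field condition. For Perceived Health Risks, Product Interest and Tobacco Policy the model is an ANCOVA adjusted for the Virtual Visit 1 score; for Withdrawal and Smoking Urges, for the Lab Visit 1 score. No carryover or within-person condition terms are included. Product Evaluation will be reported by field condition among those who selected each product, with the number rating it, and labelled as conditional on selection.

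If only Conditions 2 and 4 reach the field, state that nicotine content is the only factor, and delete flavor and the interaction both here and in the exploratory field model. If all four do, correct the statement in Virtual Visits 2-5 and keep flavor as a between-person factor. A paired pre-post change may be added if it is labelled uncontrolled.

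This costs wording only, since the scores are already scheduled. The price is between-person contrasts with less precision, limited to nicotine content if only Conditions 2 and 4 are used.

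**Route B, if within-person contrasts are wanted.** Add the scales to the assessment list for Virtual Visits 2-5. The condition terms then become estimable, at the cost of extra questionnaires at four visits.
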